#### 8.0 RISK/BENEFIT ANALYSIS

## 8.1 Anticipated Risks

No clinically significant risks are expected to occur to the subjects from interacting with and using purpleDx. The scans are non-contact and the data being generated in this study will only be used to demonstrate comparability with existing methods of data capture to support a marketing application.

Hypoallergenic tape will be used to secure the reference marker fiducials to the skin on the back of subjects' hands to enable the purpleDx Breath Scan to function. There is a very low risk of reaction to the tape at the site of adherence to the skin. If a reaction does occur, the subject will be advised to apply a cold compress for 10 to 15 minutes at a time to help alleviate any swelling or itchiness. In the case of more serious reaction, the subject will be guided to use over-the-counter medication such as calamine lotion or 1% hydrocortisone cream.

The study has no bearing on any treatment the patient may receive through their conventional clinic structure consultation or as a result of their ED visit. However, if the subject encounters any problems in using purpleDx, they may experience transient frustration and anxiety whilst trying to resolve these difficulties.

If it becomes apparent through analysis of the data generated by purpleDx in this study that the app is not suitable for any subgroup of users, this information will be used to amend the intended user description in the device specification to ensure appropriate marketing application.

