The subject will use the purpleDx device to perform the Breath Scan to measure PEF, FEV1 and RR three times. Concurrently, the CI/RN or designee will observe the subject and count the number of breaths taken during each Breath Scan and will record the results on the source document. The CI/RN will use the standard Vitalograph spirometer equipment to obtain three sets of measurements for PEF and FEV1. The subject will then use the Pulse Scan on the new device to obtain three HR readings. A standard pulse oximeter will be used concurrently to obtain three HR results. Thus, three sets of results will be produced for PEF, FEV1, RR and HR by both the standard means and by the investigational equipment. Appendices 1 and 2 provide a detailed overview of the process and the app screenshots. For details of the equipment being used in the study, see Appendix 6. The purpleDx results will be displayed on the smartphone screen. The CI/RN or designee will copy the results from the new device and the standard equipment onto the subject's paper visit records to act as the source document for the parameter values. A PDF file will subsequently be emailed to the CI/RN or designated member of the clinical study team to verify the handwritten source document results from the purpleDx Breath Scan.

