## 14.7.2 Specific Strategies

## ● For PEF and FEV₁:

- o If a patient is unable to provide three acceptable blows, the best available single reading will be used (if at least one acceptable effort exists).
- o If no valid readings can be obtained from either the new device or reference method, that data point will be recorded as **missing**.

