## 20.3.3 Instructions Screen for Breath Scan (PEF, FEV₁ and RR)

When the subject clicks on 'Breath Scan' on the Scan Selection Screen, they will be taken to the step-by-step instructions on how to properly position the smartphone and position themselves, as well as how to perform the breathing manoeuvre to complete the Breath Scan. Once the subject is correctly positioned, the app will automatically begin the scan.

[figure not shown]

The subject should breathe 'normally' for the first 4 breaths, followed by a full breath out, then a deep breath in. When they then next breathe out, it should done as forcefully and quickly as possible. At the end of the exhale, the subject should hold their breath for 5 seconds before resuming breathing as 'normal'. This is shown in the graph below.

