## 20.3.7 Results Screen for Breath Scan (PEF, FEV₁ and RR)

The three sets of results for PEF, FEV1 and RR will appear on the Results screen within 2 to 3 minutes of the measurements being taken, depending on the speed of the internet connection.

If any of the three sets of measurements have been unsuccessful and there are missing results, the CI/RN should ask the subject to repeat the Breath Scan. If there are any obvious reasons as to why the scan did not work, these will be noted by the CI/RN along with the need to perform a repeat scan. When the scan has been repeated, the results screen with be updated to include all successful measurements on the same screen.

A maximum of 3 retry Breath Scans should be attempted as needed to produce 3 results for each of the 3 parameters PEF, FEV1 and RR. If there are still missing data after 3 retry Breath Scans have been carried out, the missing results will be recorded as 'Not Available' (NA). The number of additional scans needed will be recorded.

Confirmation of the results for PEF, FEV1 and RR will subsequently be sent to the CI/RN as a PDF document for filing in the subject's medical notes to enable verification.

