# 20.5 Appendix 5: Determination of Pregnancy for Women Of Child-Bearing Potential

For the purposes of the inclusion/exclusion criteria for this clinical trial, it is not necessary to use a pregnancy test to exclude pregnancy in Women of Child-Bearing Potential (WOCBP). Since the app simply performs a non-invasive scan using the phone's camera functionality there is no risk to any subject or potential offspring. The CI/RN or designee will ask the subject if there is any possibility that they might be pregnant. If the subject thinks they may be pregnant they will be excluded from participation in the study. This is a precautionary measure as it may have a bearing on the ability of the app to produce reliable results (particularly in the second and third trimesters when lung capacity may be impinged by the developing offspring) and pregnant women have not been included in the verification and validation processes on the apps used during the developmental process of purpleDx.

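### The protocol's risk statements rest on the non-contact scan and leave out the forced breathing it requires, and nobody is required to judge medical suitability before the first forced effort

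*Protocol*

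**What the plan says.** The protocol makes three statements about risk.

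- Section 8.1: "No clinically significant risks are expected to occur to the subjects from interacting with and using purpleDx". The reason given is that the scans involve no contact. The only risks then named are a skin reaction to the marker tape and passing frustration or anxiety.
- Section 15.7: no adverse events are foreseen during device testing, because the camera scan is non-invasive.
- Appendix 5: "there is no risk to any subject or potential offspring", again because the app only performs a non-invasive scan.

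The procedures ask for physical effort. In each Breath Scan the subject breathes out fully, takes a deep breath in and exhales; of that exhalation, Appendix 3 (20.3.3) says "it should done as forcefully and quickly as possible". At the end, "the subject should hold their breath for 5 seconds before resuming breathing". The scan is done three times (7.2, 11.0), and "A maximum of 3 retry Breath Scans should be attempted" where results are missing (20.3.7). For the reference values, staff "will use the standard Vitalograph spirometer equipment to obtain three sets of measurements" of PEF and FEV1 (11.0).

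On entry, adults are approached in the Emergency Department waiting area (13.1) and may have chest or heart symptoms or none (12.1). The four exclusions in 12.2 are inability to sit up, known pregnancy, inability to comply, and being a prisoner or young offender.

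**The concern.** The forced exhalation and the breath hold are part of using purpleDx, so they fall within the scope of the section 8.1 sentence. The reason offered there, absence of contact, says nothing about them. The reference spirometry is carried out for the study and appears in none of the three risk statements.

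Eligibility does not fill the gap. A patient who is willing, has capacity, can sit up and can follow instructions may reach the first forced effort without anyone having been asked whether repeated forced expiration or breath-holding suits their present condition. The population includes acutely ill people: section 11.0 collects mortality status at 7, 14 and 30 days. Section 8.2 expects no particular clinical benefit to subjects. Section 16.7 relies on low participant risk to justify its level of peer review and the absence of a monitoring committee, so the risk description supports more than one decision.

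What is at stake is who performs the manoeuvre. It is not a statistical result.

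**Working it through.** The protocol gives no figure to reproduce on this point. The check compares sections and makes two small counts.

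**1. Risk statements against procedures**

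| Procedure | 8.1 | 15.7 | Appendix 5 |
|---|---|---|---|
| Forced exhalation in the Breath Scan (20.3.3) | not mentioned | not mentioned | not mentioned |
| 5-second breath hold (20.3.3) | not mentioned | not mentioned | not mentioned |
| Reference spirometry, 3 sets (11.0) | not mentioned | not mentioned | not mentioned |

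**2. Is there a suitability check before the first effort?** The candidates are:

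- Exclusion 3 (12.2) tests ability to comply. An able and willing patient passes it, whatever their condition.
- The capacity assessment (13.2) tests understanding.
- The pregnancy exclusion is explained in Appendix 5 by data quality: "This is a precautionary measure as it may have a bearing on the ability of the app to produce reliable results".
- Medical conditions (11.0) are recorded to characterise the intended-use population. In the schedule (13.5.1), the only part of that item tied to eligibility is pregnancy.
- The back arrow (20.3.4) stops a scan already under way that will not give a reliable result.
- Withdrawal (13.3) is at the subject's request.
- Engineering approval (Appendix 6) concerns the equipment.
- Adverse event reporting (15.1, 15.11) covers comparator and procedure events, but only after they occur.

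None of these requires a medical judgement before the first effort.

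**3. Count of efforts**

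- Planned per subject: 3 Breath Scans + 3 spirometry sets = 6, assuming one blow per set.
- Breath Scans if all retries are used: 3 + 3 = 6. Each includes one separate 5-second hold; no instructed hold is longer.
- Study total as planned: 6 × 150 = 900 to 6 × 160 = 960.
- No upper total can be given, because no cap on spirometry attempts is stated.

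These figures count exposure. They do not measure harm.

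**4. Extra consents if a check is added**

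Under 13.1, recruitment requires both a signed consent form and a study number, so a patient excluded before numbering does not use one of the 160 places. The documents give no exclusion share; 1%, 5% and 10% are assumptions. Consents needed = 160 / (1 − share), rounded up. Consent time is 15 minutes each (13.5.2).

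| Assumed share excluded | Consents needed | Extra | Extra consent time |
|---|---|---|---|
| 1% | 160 / 0.99 = 161.6 → 162 | 2 | 2 × 15 = 30 min (0.5 h) |
| 5% | 160 / 0.95 = 168.4 → 169 | 9 | 9 × 15 = 135 min (2.25 h) |
| 10% | 160 / 0.90 = 177.8 → 178 | 18 | 18 × 15 = 270 min (4.5 h) |

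**The case against.** The strongest reply is that no hazard has been shown. Nothing in the protocol describes forced expiration or a 5-second hold as unsafe for any group, and leaving a procedure out of a risk section does not prove the section's conclusion wrong. This stands. A reader might infer that the trial exposes patients to a known danger, or that the sponsor never assessed these manoeuvres. The documents support neither. Section 15.6 refers to a risk analysis report, and 13.2 expects subjects to understand the study's risks before consenting; neither the report nor the patient information sheet is shown, and either may cover the point.

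Two points about wording are also fair. The Appendix 5 sentence explains why no pregnancy test is needed and is not the study's risk assessment. The quoted sentence in 8.1 is about purpleDx, so reference spirometry lies outside it. But the forced exhalation and hold lie inside it, and spirometry is not taken up elsewhere in 8.1 or in 15.7.

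Staff discretion is real but informal. Exclusion 3 is broadly worded, consent is signed in front of the chief investigator or a designee, and a full set of efforts is not insisted on: "If a patient is unable to provide three acceptable blows, the best available single reading will be used", provided one acceptable effort exists (14.7.2). These provisions limit repetition or rely on individual initiative. None of them requires a judgement beforehand, and a risk report held by the sponsor does not put a criterion into 12.2 for site staff to apply.

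It is also correct that the protocol does not establish that the presentation code and medical history are in hand before the first manoeuvre. A check would therefore need an order of steps as well as a criterion.

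**Conclusion.** The point holds for the protocol text in two parts. The three risk statements rest on the nature of the scan and omit the forced exhalation, the breath hold and the reference spirometry. And no criterion, schedule item or consent step requires a judgement of medical suitability before the first forced effort.

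The size that can be stated is exposure: 6 planned efforts per subject, on the assumption of one blow per spirometry set. No rate or severity of harm can be derived, so the totals should not be read as a safety estimate. The wording gap alone would be a matter of documentation. The missing check is the part that could affect patients. Overall this is a cheap improvement of modest severity, and it leaves the agreement analysis and the sample size calculation unchanged.

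**What to change.** **1. Eligibility, the change that matters.** Add to 12.2: *any condition that, in the opinion of the chief investigator or delegated clinician, makes repeated forced expiration or breath-holding unsuitable.* Require the relevant medical conditions and the presentation code, both already collected under 11.0, to be taken after consent and before study number assignment and the first manoeuvre, so that the person deciding has the information. Keep an anonymous count of exclusions with reasons, and report it beside the 10.2 endpoint on patient subsets for which the device may be unsuitable. Section 13.3 needs no change, because it governs withdrawal by the subject and not exclusion by a clinician.

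**2. Accompanying wording.** Name the forced exhalation, the breath hold and the reference spirometry in 8.1 and 15.7, and remove the no-risk statement from Appendix 5. Keep the text consistent with the risk analysis report and the patient information sheet.

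**Cost.** One brief check per consented subject, whose duration the documents do not give, plus the extra consents tabulated above. The site is reimbursed on signed consent (Appendix 11), so the sponsor pays for consented patients who are not tested. The results, including the search for unsuitable subgroups, would apply only to patients judged suitable for forced expiration, which is why the exclusions should be reported with that endpoint.

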#### 8.2 Potential Benefits

There are no particular clinical benefits for the subjects that take part in this clinical investigation, and there is no financial inducement to participate in the study. However, the subject may feel increased self-esteem or sense of altruism from participating in research that could potentially bring about improved management of respiratory or cardiopulmonary patients in the future.

#### 9.0 STUDY OBJECTIVES

## 9.1 Primary Objectives

The primary objectives of this study are to determine whether the purpleDx non-interventional smartphone technology measures patients' peak expiratory flow (PEF), forced expiratory volume in one second (FEV1), respiratory rate (RR) and heart rate (HR) within an acceptable agreement range and margin when compared to results measured using standard clinical testing equipment, and to demonstrate ease of use of purpleDx as opined by subjects and clinical staff.

## 9.2 Secondary Objectives

The secondary objectives of this study are to demonstrate the safety and usability of purpleDx in the Emergency Department setting, whether there are any subject subgroups or conditions of use for which purpleDx fails to generate sufficiently reliable data and establishment of thresholds for 'normal' ranges for PEF, FEV1, RR and HR.

#### 10.0 STUDY ENDPOINTS

#### 10.1 Primary Endpoint

• Determination of the agreement in measurement of physiological signals of peak expiratory flow by traditional medical equipment and purpleDx to enable marketing application.

### 10.2 Secondary Endpoints

- Determination of the agreement in measurement of forced expiratory volume in one second, heart rate and respiratory rate by traditional medical equipment and purpleDx.
- Establishment of thresholds for 'normal' ranges for peak expiratory flow, forced expiratory volume in one second, respiratory rate and heart rate.

- Evaluation of the ease of using the User Interface and demonstration of usability by subjects and clinical staff.
- Demonstration of the safety of purpleDx.
- Determination of any subsets of the patient population for which purpleDx may not be suitable.
- Determination of any conditions or situations which impair the recording quality or reliability of data produced by purpleDx that have not already been determined during pre-clinical testing.

#### 11.0 STUDY DESIGN

This study will take place at a single investigational site, namely Cambridge University Hospitals NHS Foundation Trust (CUH) in the Emergency Department, where the research team has extensive experience in performing clinical research studies in similar fields. The study will be conducted in compliance with the protocol, principles of Good Clinical Practice (GCP) and the applicable regulatory requirements.

Subjects will be male or female, aged 18 years and above. Subjects must be able to sit up and read, understand and write in English. Subjects with and without respiratory or cardiorespiratory symptom/s will be included. All participants will be required to sign an Informed Consent Form (ICF) and be allocated a unique study number by the Chief Investigator (CI)/Research Nurse (RN) or a suitably trained designee. Subjects will only be identified by the study number in all trial-related documentation i.e. there will be no patient identifiable information (PID) recorded for study purposes. At the hospital site, a subject identification log will be maintained to link the study subject number to individual PID, which will only be accessible to the subjects' clinical research team. This information will not be made available to the Sponsor. However, the study monitor will require access to ensure the correct subject's medical notes are reviewed during source data verification (SDV). The subjects will be made aware of this during the informed consenting process.

There are no treatment arms in the study. Each subject will be tested using standard clinical equipment to produce control data and by purpleDx to produce investigational data.

At the hospital visit, the following data points will be collected for each subject by the CI/RN or designee:

- Unique Subject Study Number
- Sex at birth
- Age in years

- Date of assessment
- Height in cm
- Weight in kg
- Chest circumference in cm (see Appendix 7)
- Skin tone (measured using device provided by Sponsor); see Fitzpatrick scale in Appendix 4
- Emergency Care Data Set (ECDS) presentation code
- Discharge diagnosis confirming chest illness
- 7, 14 and 30-day mortality status
- Smoking status (and number of pack years if smoker)
- Medical conditions (up to 5 relevant respiratory or cardiorespiratory) conditions, cardiac conditions, skeletal conditions e.g. scoliosis / mobility problems) to describe the population for intended use
- Confirmation of no known pregnancy in women of child-bearing potential (WOCBP); see Appendix 5
- Light Level (measured using device provided by Sponsor)
- Sitting or Reclining (and angle of recline if reclining)
- Peak expiratory flow (PEF) measured by purpleDx
- Peak expiratory flow (PEF) measured by conventional equipment (provided by Sponsor)
- Forced expiratory flow in one second (FEV1) measured by purpleDx
- Forced expiratory flow in one second (FEV1) measured by conventional equipment
- Respiratory rate (RR) measured by purpleDx
- Respiratory rate (RR) measured by manual count / visual inspection
- Heart rate (HR) measured by purpleDx
- Heart rate (HR) measured by conventional equipment
- Nurse/clinician assessment of subjects' ability to use purpleDx
- Subject evaluation of ease of using purpleDx
- Difficulties using purpleDx
- Adverse Event information
- Confirmation of new disposable mouthpiece for each subject's spirometry assessments.

During each purpleDx measurement, the following will also be recorded by the CI/RN or designee:

- Participant behaviour during recording, such as movement, talking, coughing,
- Facial obstructions, such as glasses, hats, beards, makeup, etc
- Chest obstructions, such as lanyards, loose clothing, top pattern (uniform versus patterned), etc
- Specific technical difficulties that may be encountered

[figure not shown]

Details of any difficulties in following instructions.

The CI/RN or designee will use the light meter (see details in Appendix 6) provided by the Sponsor to ensure lighting levels are in the required range to allow purpleDx to function and will demonstrate how to use the purpleDx app to the subject. The Sponsor will provide the site with an iPhone containing the purpleDx app already downloaded and ready for use.

The subject will use the purpleDx device to perform the Breath Scan to measure PEF, FEV1 and RR three times. Concurrently, the CI/RN or designee will observe the subject and count the number of breaths taken during each Breath Scan and will record the results on the source document. The CI/RN will use the standard Vitalograph spirometer equipment to obtain three sets of measurements for PEF and FEV1. The subject will then use the Pulse Scan on the new device to obtain three HR readings. A standard pulse oximeter will be used concurrently to obtain three HR results. Thus, three sets of results will be produced for PEF, FEV1, RR and HR by both the standard means and by the investigational equipment. Appendices 1 and 2 provide a detailed overview of the process and the app screenshots. For details of the equipment being used in the study, see Appendix 6. The purpleDx results will be displayed on the smartphone screen. The CI/RN or designee will copy the results from the new device and the standard equipment onto the subject's paper visit records to act as the source document for the parameter values. A PDF file will subsequently be emailed to the CI/RN or designated member of the clinical study team to verify the handwritten source document results from the purpleDx Breath Scan.

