#### 13.4 Randomisation

This is not applicable to this clinical trial as all subjects undergo the same testing process and are not assigned to treatment arms. Each subject will act their own control, by being tested with standard clinical equipment and the SaMD.

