## 16.5.2 Patient Confidentiality

To maintain patient confidentiality, the subjects who take part in this clinical study will each be identified by a study number that will consist of a sequence of seven numbers that are randomly generated (by the Vitalograph spirometer) and assigned completely independently of the patient details. The study number will replace all Patient Identifiable Data (PID) for the purposes of the study, and the Sponsor will have no access to PID.

The clinical site will maintain a subject log with details to link the study number to a specific patient. This log will not be kept in the Investigator Site File (ISF) and will not be accessible by the Sponsor but will be used by the monitor to ensure the correct subject medical notes are reviewed for the purposes of SDV. The log containing the linking code to individual patients will be securely stored in a password protected and encrypted digital file, in a separate location to any study data. During the informed consent process, subjects will be made aware of the need for the external review of PID in their hospital medical records for the monitoring process, to validate the depersonalised data for the study. It will be reiterated that no PID will be held in the study databases or accessible by the Sponsor. In this respect, the clinical site remains the data custodian in terms of any PID, whilst the Sponsor is responsible for the depersonalised data collected for study purposes as defined in this protocol.

Each subject will be required to provide consent for the Sponsor's monitor to access their PID solely for monitoring purposes. The ISF will be kept secure in a locked office only accessible by members of the site study team.

Although there is no patient identifiable data in this study, there is the potential for identifiable details to be sent to the Sponsor in error (e.g. on an email). Accordingly, methodology is in place to handle such a scenario.

If a breach of patient confidentiality occurs, the person discovering the breach must contact the Sponsor's designated Data Protection Officer (DPO) within 24 hours of discovery to inform them of the details. The Sponsor will then act in accordance with their internal Data Security and GDPR Compliance procedure.

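### PEF and FEV1 appear to be measured by purpleDx first and spirometry second in everyone, so mean bias mixes device bias with any order effect

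*Protocol*

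**What the plan says.** Section 11.0 of the protocol sets out the measurements in one paragraph. It opens with "The subject will use the purpleDx device to perform the Breath Scan to measure PEF", along with FEV1 and RR, three times over, while staff count breaths at the same time. It continues, for PEF and FEV1: "The CI/RN will use the standard Vitalograph spirometer equipment to obtain three sets of measurements". Next comes "The subject will then use the Pulse Scan on the new device to obtain three HR readings", and for that step "A standard pulse oximeter will be used concurrently to obtain three HR results".

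Section 13.4 treats randomisation as not applicable because "all subjects undergo the same testing process and are not assigned to treatment arms".

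Appendix 3 (20.3.3) shows that each Breath Scan contains a forced exhalation: "it should done as forcefully and quickly as possible". Section 20.3.7 allows up to three retry Breath Scans. Section 14.2 takes the best effort of three for PEF and FEV1 on each method. Section 14.3.1 plans a Bland-Altman mean difference with limits of agreement, and the table in 14.3.5 gives PEF a bias target of ±10%.

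The visible text does not randomise, alternate or counterbalance the order of the two methods, and order is not among the data items listed in 11.0.

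**The concern.** For RR and HR, device and reference observe the same minute, so nothing can change between them. For PEF and FEV1 the two methods use different forced efforts. On the order narrated, three to six forced exhalations with purpleDx come before the first spirometer blow. If subjects tire, or learn the manoeuvre, the change falls on the reference value in every subject.

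With a single order, the mean paired difference estimates device bias plus order effect. More subjects narrow the interval around that sum but do not split it. Having no treatment arms, the reason given in 13.4, does not settle the matter, because the order of two methods can be allocated within a single-group paired study.

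The stake is the primary parameter of a study meant to support a marketing application. An order effect in the opposite direction to a real device bias would make the device look better than it is, and the report would give no sign of it.

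**Working it through.** **1. The plan's own figure.** Section 14.4.1 uses p0 = 0.80, p1 = 0.90, two-sided α = 0.05 and power 0.90:

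n = [1.96·√(0.8·0.2) + 1.2816·√(0.9·0.1)]² / (0.10)² = 136.5, rounded up to 137. This reproduces the plan.

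Under the Wilson rule of 14.3.2 with 137 subjects, 118 successes give a lower bound of 0.794 and 119 give 0.802, so a pass needs at least 119/137. The exact binomial pass probability is 0.024 at p = 0.80 and 0.91 at p = 0.90.

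**2. What each design can estimate.** Let B be the device bias and o the order effect, both as a percentage of the reference.
- One order for all: the mean difference estimates B + o, at any n.
- Two orders, half the subjects each: the sequence means estimate B + o and B − o. Their average gives B and half their difference gives o.

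**3. Assumption needed for a size.** The documents give neither a size nor a direction for o. I assume percentage differences are normal, with the SD set so that 90% fall within ±20% at zero bias: SD = 20/1.645 = 12.16%. With total shift s,

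P(within ±20%) = Φ((20 − s)/12.16) − Φ((−20 − s)/12.16).

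Under this SD and two orders, B and o each have a standard error of 12.16/√137 = 1.04 percentage points (95% half-width about 2.0).

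**4. Masking.** Take B = 9.4%. Then P = Φ(0.872) − Φ(−2.418) = 0.80, and the chance of passing at n=137 is about 0.025. Now add an order effect in the opposite direction:

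| Order effect | One order: P within ±20% | One order: chance of passing | Counterbalanced: P within ±20% | Counterbalanced: chance of passing |
|---|---|---|---|---|
| 2% | 0.838 | 0.20 | 0.797 | 0.02 |
| 3% | 0.853 | 0.36 | 0.792 | 0.014 |
| 5% | 0.878 | 0.69 | 0.776 | 0.0045 |

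Example for 5%: under one order s = 9.4 − 5 = 4.4 and P = 0.878. Counterbalanced, half the subjects have s = 4.4 (0.878) and half have s = 14.4 (0.675), which averages 0.776.

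**5. Unbiased device.** With B = 0 and one order, o = 5% gives P = 0.871 and power 0.60; o = 8% gives P = 0.828 and power 0.12. A +5/−5 or +8/−8 split gives the same proportions and the same power, because the ±20% band is symmetric around zero.

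**The case against.** The strongest objection is that the fixed order is inferred. The sentence on spirometry has no sequence word; the word marking sequence belongs to the Pulse Scan. Section 13.4 explains why there are no arms and does not prescribe a device order. Figure 1 (the visit overview) and the Appendix 1 workflow diagram, where order would most likely appear, are missing from the text at hand. A reader might infer that the protocol expressly fixes purpleDx first; the visible text does not say so. What stands is that this is the natural reading of the narrative and that nothing visible counterbalances. If order is in fact left open, it is uncontrolled and, on the listed data items, unrecorded, so it still could not be separated.

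Second, no order effect is documented. Learning and fatigue act in opposite directions, best-of-three may dampen learning, and each forced effort sits inside a one-minute scan, which spaces the efforts. These features may reduce the effect. They do not remove a shift between the two methods.

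Third, a reader might infer that counterbalancing would rescue power. Step 5 of the working shows that it would not for an unbiased device.

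Fourth, it would be too strong to say that the data are silent on order. Trends across the three readings, or bias by number of retry scans, could be explored. Neither identifies the shift between methods.

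**Conclusion.** The point holds as a design weakness affecting PEF and FEV1 only. As narrated, mean bias and the position of the limits of agreement combine device bias with any order effect, and the planned analyses cannot separate them. RR and HR are not affected, and the sample size of 137 is correct and unchanged.

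The practical risk is a false pass. Under the assumed SD of 12.16%, a device whose true bias of 9.4% puts it at the 80% threshold would pass with probability 0.20 to 0.69 if an opposing order effect of 2 to 5% were present, against about 0.02 or less with counterbalancing. These are illustrations over an assumed range. They rest on normal errors and on carry-over being the same in both directions, and they do not show that an order effect exists. The change is worth making because it is cheap and because an order effect cannot be removed once the data are collected, but it does not invalidate the design.

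**What to change.** In 11.0 and 13.4, state that the order of Breath Scans and spirometry is allocated by the parity of the study number. Section 16.5.2 already describes this number as a "sequence of seven numbers that are randomly generated (by the Vitalograph spirometer"). It is assigned after consent (13.1) and entered in the app before scanning (20.3.1), so it is available in time. Bring Figure 1 and the Appendix 1 diagram into line with this text.

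Record the order actually used. Report Bland-Altman bias and the within-20% proportion overall and by order, with half the between-order difference in mean bias as the estimated order effect.

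The cost is one line in each of two sections, one tick-box and slightly more complex visits, with no extra subjects or measurements. Three limits should be stated:
- An order effect would widen the pooled spread, and the within-20% proportion and power it costs an unbiased device are not restored.
- Averaging the two orders isolates device bias only if carry-over is symmetric. Three spirometer blows beforehand may not equal three to six Breath Scans beforehand.
- Half the subjects would rate purpleDx usability after practising forced efforts on the spirometer, so usability should also be shown by order.
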